8.8 Twenty-four (24) month in-person visit

All subjects will return to the enrolling site approximately 24 months (visit window of 24 months +/- 4 weeks) after enrollment and will complete the following:

- Quality-of-life questionnaires
- Spirometry and an DLCO assessment
 - *If a spirometry (with DLCO) assessment is available within 90 days of the in-person visit it may be used as the study assessment. Otherwise the spirometry assessment with DLCO should be conducted at the in-person visit.
- Blood draw for the following safety labs (for antimicrobial arm only):
 - Chemistry panel and liver function tests– defined as minimum of sodium, potassium, chloride, bicarbonate, BUN, and creatinine, total bilirubin, direct bilirubin, alkaline phosphatase, ALT, and AST
- Complete Blood Count (CBC) (for antimicrobial arm only)
- Blood draw for gene expression
- Buccal and fecal samples collection for microbial ecology

8.9 Thirty (30) month phone contact

Approximately 30 months (visit window of 30 months +/- 4 weeks) after enrollment, subjects will be contacted by the site coordinator to document the following:

- Vital status
- Medication adherence
- Hospitalization and respiratory infection information

8.10 Thirty-six (36) month phone contact

Approximately 36 months (visit window of 36 months +/- 4 weeks) after enrollment, subjects will be contacted by the site coordinator to document the following:

- Vital status
- Medication adherence
- Hospitalization and respiratory infection information

Participants randomized to the antimicrobial arm who are still taking study drug at this visit should consult with their treating pulmonologist about continuing any prescriptions for antimicrobial therapies, as prescription drug voucher coverage will cease after completion of the 36 month phone contact. Data collection for study purposes will cease after completion of the 36-month phone contact.

9. OUTCOME DETERMINATIONS

9.1 Primary Endpoint

The primary endpoint of this study will be the time to first non-elective, respiratory hospitalization or all-cause mortality.

9.2 Secondary Endpoints

- Time to death from any cause
- Time to first non-elective respiratory hospitalization
- Time to first non-elective all-cause hospitalization
- Total number of non-elective respiratory hospitalizations
- Total number of non-elective all-cause hospitalizations
- Change in FVC from randomization to 12 months
- Change in DLCO from randomization to 12 months
- Total number of respiratory infections
- Change in UCSD-Shortness of Breath Questionnaire from randomization to 12 months
- Change in Fatigue Severity Scale score from randomization to 12 months
- Change in Leicester Cough Questionnaire score from randomization to 12 months
- Change in EQ-5D score and SF-12 score from randomization to 12 months
- Change in ICEpop CAPability measure for Older people (ICECAP-O) score from randomization to 12 months

9.3 Role of the CleanUP-IPF Adjudication Committee

An Adjudication Committee will classify all hospitalization events. The Adjudication Committee will follow procedures described in the Adjudication Charter. Briefly, medical records from inpatient hospitalizations will be obtained by the data coordinating center through an established, secure process which will be detailed in the informed consent document. Non-elective respiratory hospitalizations will be defined as any unplanned inpatient hospitalizations for which the primary cause was a pulmonary condition, in the opinion of the blinded adjudicators and based on all available clinical data. Examples include, but are not limited to, the following:

- acute exacerbation of IPF (definite or suspected)
- pulmonary infection/pneumonia
- pulmonary embolus
- pneumothorax
- pulmonary aspiration
- ARDS of identifiable cause

These causes will be adjudicated by review of admission history and physical and discharge summary from the hospitalization. These documents will be obtained (with patient consent) by the DCC from the hospital where the encounter occurred. Documents will be made available to adjudicators in PDF form via the secure and integrated data management system (IBM Clinical Development Endpoint Adjudication Module) at the DCC. Each hospitalization event will be adjudicated by one of the study pulmonologists from the adjudication committee, ensuring that the adjudicator is independent from the study site at which the event occurred. If this adjudication is in agreement with the site investigator’s assessment (with regard to date of event, elective vs. non-elective and respiratory vs. non-respiratory), this assessment will serve as the final event adjudication. In the event of the independent adjudicator’s assessment disagreeing with the site investigator’s assessment, a second blinded member of the adjudication committee, also independent of the involved site, will serve as a “tiebreaker”.

Hospitalizations occurring primarily for lung transplantation will be considered “elective,” as the timing of lung transplant events is unpredictable because of donor lung availability rather than occurrence of acute or worsening illness. On the other hand, hospitalizations initially caused by an acute pulmonary condition but during which lung transplantation later occurs will be considered non-elective. Non-pulmonary causes of dyspnea, such as cardiac disease, will not be considered respiratory causes of hospitalizations.

10. PARTICIPANT SAFETY AND ADVERSE EVENTS

10.1 Institutional Review Boards

All CleanUP-IPF sites will submit the study protocol, informed consent form, and other study documents to their IRB for approval—the approval letter for each clinical center will be stored at the CC. Any amendments to the protocol, other than minor administrative changes, must be approved by each IRB before they are implemented.

10.2 Informed Consent

All patients will have the purpose of the study, the study interventions and evaluations, and the potential risks and benefits of participation explained to them and their questions answered. If they consent to participation in this study, they will review and sign the informed consent form.

10.3 Summary of the Risks and Benefits

This study will evaluate an antimicrobial therapy strategy in patients with IPF. These agents are currently used in clinical practice. We therefore do not anticipate that participation in this study will be associated with increased risks beyond that of standard IPF therapy. We have added limited exclusionary criteria to minimize risk of antimicrobial therapy.

Potential benefits to study participants include the possibility of improvements in clinical outcomes.

10.4 Adverse Events

Adverse events (AEs) of special interest ONLY will be collected for the CleanUP-IPF trial. These AEs include:

- Arrhythmia
- Vomiting
- Diarrhea
- Rash
- Hyperkalemia

These adverse events of special interest will be collected via data entry into the eCRF within the electronic data capture system. Start and stop dates will also be collected for these events, as well as any concomitant medications prescribed (with start and stop dates of the concomitant medication) for treatment of such events.

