5. TREATMENT INTERVENTIONS

This will be an unblinded, randomized clinical trial comparing the following treatment strategies

- Standard care
- Standard care + oral antimicrobial therapy

Patients randomized to receive antimicrobial therapy will receive a prescription drug voucher for the medication (and folic acid if given co-trimoxazole) during the enrollment visit. To minimize risk to the participating subject and to maximize a positive outcome we have created an algorithm for antimicrobial therapy that encourages use of co-trimoxazole but allows doxycycline use.

[figure not shown]
Figure 1 illustrates the proposed antimicrobial therapy algorithm. Contraindications to co-trimoxazole at enrollment include:

- allergy to sulfa products or trimethoprim
- renal insufficiency (GFR < 30 mL/min, defined as estimated from the blood urea nitrogen and creatinine)
- hyperkalemic (potassium > 5 mEq/L)
- concomitantly taking an ACEI, ARB, potassium sparing diuretic, dofetilide, methotrexate, azathioprine, mycophenolate mofetil, cyclophosphamide
- Other contraindication to co-trimoxazole in the investigator's opinion

Subjects meeting any of the above and randomized to antibiotic therapy will take doxycycline instead. Subjects on vitamin A or retinoids will need to stop these medications if randomized to doxycycline.

Co-trimoxazole intolerance is defined by the investigator. Mild intolerance (e.g. nausea, abdominal pain, headaches, anorexia) may require a dose adjustment to half dose. Moderate intolerance (e.g. decreased leukocytes, mild increase in potassium) require a dose adjustment or a switch to doxycycline at the investigator's discretion. A significant intolerance (e.g. leukopenia, hyperkalemia, decrease in GFR by more than 50% or to less than 30 ml/min, rash) requires stopping the co-trimoxazole and providing medical treatment as appropriate. Doxycycline should be started when medically appropriate in the opinion of the investigator after moderate or significant intolerance. All dose adjustments will be at the discretion of the treating physician(s) with the medical monitor available for consultation if needed. Dosing adjustments, and/or switching of co-trimoxazole to doxycycline, will be documented within the eCRFs, as well as the reason for the adjustment.

Figure 1

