8.2 One (1) month phone contact

Approximately 1 month (visit window of 1 month +/- 7 days) after enrollment, all subjects will be contacted by the site coordinator to document the following:

- Any issues related to drug assignment
- Vital status assessment
- Medication adherence
- Hospitalization and respiratory infection assessment

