8.6 Twelve (12) month in-person visit

All subjects will return to the enrolling site approximately 12 months (visit window of 12 months +/- 4 weeks) after enrollment and will complete the following:

- Quality-of-life questionnaires
- Spirometry and DLCO assessment
 - *If a spirometry (with DLCO) assessment is available within 90 days of the in-person visit it may be used as the study assessment. Otherwise the spirometry assessment with DLCO should be conducted at the in-person visit.
- Blood draw for the following safety labs (for antimicrobial arm only):

- Chemistry panel and liver function tests– defined as minimum of sodium, potassium, chloride, bicarbonate, BUN, and creatinine, total bilirubin, direct bilirubin, alkaline phosphatase, ALT, and AST
- Complete Blood Count (CBC) (for antimicrobial arm only)
- Blood draw for gene expression
- Buccal and fecal samples collection for microbial ecology

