Concomitant Medication Review	X										
Concomitant Medication Update			X			X	X	X	X	X	X

Complete Blood Count (CBC)	X (if not available in last 90 days)			X ³	X ³		X ³		X ³		
Chemistry panel w/liver function tests	X (if not available in last 90 days)			X ³	X ³		X ³		X ³		
Electrolytes only		X ²									
Genotype	X										
Gene expression	X						X		X		
Buccal Swab, Fecal samples	X						X		X		
Patient Reported Outcomes Questionnaires ¹	X						X		X		
Clinical Events			X			X	X	X	X	X	X
Mortality			X			X	X	X	X	X	X
Hospitalization			X			X	X	X	X	X	X
Resp. infection			X			X	X	X	X	X	X

1. Patient reported questionnaires include: UCSD-SoBQ, Fatigue Severity Scale, Leicester Cough, EQ-5D, SF-12, ICECAP-O
2. For subjects receiving co-trimoxazole, a blood sample to document electrolytes will be drawn at week 1, Visit 1A.
3. For subjects assigned to the antimicrobial therapy arm, a blood sample to document complete blood count, liver function tests, and chemistry panel, will be drawn at 3 months, 6 months, 12 months, and 24 months to be obtained at Visit 2A, Visit 2B, Visit 4, and Visit 6, respectively.

16. APPENDIX B – CleanUP-IPF Laboratory Schedule

Antimicrobial Arm (Co-trimoxazole and Doxycycline Arms)

	CBC	Electrolytes	Chemistry plus liver function tests	Gene expression	Genotype	Buccal sample	Fecal sample	Approx. total Blood Amount
Baseline	x		x	x	x	x	x	28.5 ml
Week 1		x*						6 ml
3 month	x		x					8.5 ml
6 month	x		x					8.5 ml
12 month	x		x	x		x	x	18.5 ml
24 month	x		x	x		x	x	18.5 ml
*only in co-trimoxazole treated patients								88.5 ml

Standard of Care Arm

	CBC	Chemistry plus liver function tests	Gene expression	Genotype	Buccal sample	Fecal sample	Approx. total Blood Amount
Baseline	x	x	x	x	x	x	28.5 ml
12 month			x		x	x	10 ml
24 month			x		x	x	10 ml
							48.5 ml

Safety Labs

Complete Blood Count (CBC): WBC, RBC, hemoglobin, hematocrit, mean corpuscular volume (MCV), Platelets, mean platelet volume (MPV)

Electrolytes: Sodium, Potassium, Chloride, Carbon Dioxide (CO₂)

Chemistry: Sodium, Potassium, Chloride, Carbon Dioxide (CO₂), Urea Nitrogen (BUN) and Creatinine

Liver Function Studies: Alkaline Phosphatase, Total Bilirubin, Direct bilirubin, Aspartate Aminotransferase (AST), and Alanine Aminotransferase (ALT)

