### **Serious adverse events**

Endpoint Description: Frequency and types of serious adverse events (SAEs) during the following-up period of the trial.

Response Variable Definition: SAEs will be identified by the site PI and coded into the MEDRA medical dictionary.

Statistical Tests: The number of patients with one or more SAEs will be tabulated along with the total number of distinct SAEs. Comparison of the “Standard care + oral antimicrobial therapy” and “Standard care” arms will be done with a chi-square test, i.e. the number of patient with one or more events. Other groupings of SAEs maybe generated as deemed necessary.

Interpretation of Results: For cases where “Standard care + oral antimicrobial therapy” rate is less than “Standard care” rate will indicate a reduction for “Standard care + oral antimicrobial therapy” arm. For cases where “Standard care + oral antimicrobial therapy” rate is greater than “Standard care” rate will indicate an increase for “Standard care + oral antimicrobial therapy” arm.

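### Non-serious leukopenia and GFR decline, which Section 5 names as reasons to stop co-trimoxazole, are not on the Section 10.4 AE list, and the SAP plans no summary of the safety labs, dose-change reasons or listed AEs

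*Protocol*

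**What the plan says.** **Collection.** Protocol Section 10.4: "Adverse events (AEs) of special interest ONLY will be collected for the CleanUP-IPF trial". The list is arrhythmia, vomiting, diarrhea, rash and hyperkalemia. Section 10.5 separately captures every SAE, including any found by a laboratory test.

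**Stop and change reasons.** Protocol Section 5: "A significant intolerance (e.g. leukopenia, hyperkalemia, decrease in GFR by more than 50% or to less than 30 ml/min, rash) requires stopping the co-trimoxazole". One step lower: "Moderate intolerance (e.g. decreased leukocytes, mild increase in potassium) require a dose adjustment or a switch to doxycycline at the investigator's discretion". Section 5 also has dose adjustments and switches to doxycycline entered in the eCRF with their reason.

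**Laboratory schedule.** Appendix A, footnote 3, says of antimicrobial-arm patients: "a blood sample to document complete blood count, liver function tests, and chemistry panel, will be drawn at 3 months, 6 months, 12 months". The last scheduled draw is at month 24. Section 8.6 marks the arm restriction at month 12: "Complete Blood Count (CBC) (for antimicrobial arm only". Standard care has these panels at baseline only.

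**Reporting.** SAP IX has two safety endpoints. One is "Frequency and types of serious adverse events (SAEs) during the following-up period of the trial"; the other is concomitant medication. The safety shells are Tables 5.1 and 5.2.

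**The concern.** The protocol treats a fall in white cells and a fall in GFR as serious enough to end co-trimoxazole, and it draws blood that could show both. Yet neither has an AE term unless it becomes an SAE, and nothing in the SAP turns the blood results or the recorded reasons into a summary. The comparison is of a long-term antibiotic strategy with standard care alone, so tolerability is part of the answer. The sponsor's termination letter, appended to the SAP, reports no clear harm signal but a trend toward more SAEs in the intervention arm. A reader will then want to know how often patients had to reduce, switch or stop co-trimoxazole, and why. As written, the plan does not commit to telling them.

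**Working it through.** No figure in the plan needs reproducing. The check sets the passages side by side.

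**1. Section 5 stop examples against the Section 10.4 list**

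| Section 5 significant intolerance | On the 10.4 list? |
|---|---|
| Leukopenia | No |
| Hyperkalemia | Yes |
| GFR decline (numeric criterion given) | No |
| Rash | Yes |

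Two of four are missing. The milder leukocyte fall under moderate intolerance is missing too. The month-1 call asks about "Any issues related to drug assignment", so an unlisted effect may be mentioned there, but Section 10.4 gives it no AE field.

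**2. What is drawn, and in whom**

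- Antimicrobial arm: CBC, chemistry with BUN and creatinine, and liver tests at months 3, 6, 12 and 24, which is four post-baseline draws.
- Standard care: none after baseline.
- Week 1, co-trimoxazole patients only: electrolytes, with no CBC or creatinine.

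Appendix B's blood volumes agree. Antimicrobial arm: 28.5 + 6 + 8.5 + 8.5 + 18.5 + 18.5 = 88.5 ml, as stated. Standard care: 28.5 + 10 + 10 = 48.5 ml, as stated. The gap at months 12 and 24 is 18.5 − 10 = 8.5 ml each time, which equals the month-3 draw of CBC plus chemistry.

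**3. What the SAP does with each source**

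| Source | Planned SAP summary |
|---|---|
| SAEs | Table 5.1, by body system and event |
| Concomitant medication | Table 5.2 |
| Five listed AEs | None |
| Reasons for dose change or switch | None |
| Post-baseline safety labs | None |

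Three near misses do not fill the gap. SAP X estimates therapy distribution and adherence. Table 1.2 gives reasons for withdrawal from the study. Table 5.2 has a co-trimoxazole row showing use or non-use. None gives the reason for a drug change.

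**4. Number of panels as planned**

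Assume about 250 patients in the antimicrobial arm (500 randomized 1:1), uniform accrual over 30 months, and study close 12 months after the last enrolment, at month 42. A month-24 visit then needs enrolment by month 18, a fraction of 18/30 = 0.60. Panels: 250 × 3 + 250 × 0.60 = 900. This is an upper figure: it ignores deaths and withdrawals, and the trial closed early.

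**The case against.** The strongest case is that little is really lost. Serious marrow or renal events are captured whatever their name, including events that threaten health without an admission, and Table 5.1 reports them. Dose changes and switches leave an eCRF record. SAP IV promises listings of study data, and SAP XV says the shells may be modified. A short AE list is a reasonable choice in a pragmatic trial of agents already in clinical use, and one-arm labs may be drawn chiefly to manage patients.

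Much of this stands, and it rules out the stronger inference that these harms are measured and never reported. The documents support only that there is no planned summary of the non-serious cases.

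Two further inferences also fail. Because liver tests are drawn, a reader might take liver effects to be a stop reason, but Section 5 names no hepatic effect at any grade. A reader might also attach a precision to an incidence based on all 250 antimicrobial-arm patients. The Section 5 criteria apply to co-trimoxazole, some patients start on doxycycline, and the documents give neither the split nor an expected incidence.

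The objection does not explain why two of the protocol's own four stop examples are absent from a list described as exhaustive. Nor does it explain why even the five listed AEs have no table. A generic promise of listings names no laboratory value and no AE. A patient can also be taken off co-trimoxazole for a low white count or falling GFR without meeting any SAE criterion.

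**Conclusion.** The concern holds in a limited form. Two of the four Section 5 examples of significant intolerance have no AE term unless serious. Three sources bearing on tolerability (the listed AEs, the reasons for dose change or switch, and the antimicrobial-arm labs) have no planned summary. Only SAE-qualifying cases reach a planned safety table. The primary efficacy analysis is unaffected; what suffers is the completeness of the safety account.

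This rests on the SAP text and shells as published. The documents do not say whether follow-up lab values are entered in the study database. Section 5 mentions recording adjustments and switches with reasons, but does not expressly mention a stop without a switch. Both points should be confirmed. Even if tabulated, the labs describe one arm and give no randomized comparison.

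**What to change.** **Protocol.** Reconcile Section 10.4 with Section 5 so that leukopenia and GFR decline are recorded when they lead to a dose change, switch or stop. This concerns recording only; no change to any clinical stopping rule is proposed. Collection cannot now be altered in the closed trial, but the tables below can still be added from data already held.

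**SAP IX.** Add:

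1. A table of the listed AEs of special interest by arm, with a note that hyperkalemia is looked for by scheduled labs in one arm only.
2. An antimicrobial-arm table of co-trimoxazole dose reductions, switches and stops by recorded reason.
3. A descriptive antimicrobial-arm summary of CBC and creatinine/GFR, as values and changes from baseline by scheduled visit, with liver tests as values only. Count patients meeting the Section 5 criterion for GFR alone, since Section 5 gives no leukocyte threshold and no liver criterion. State the formula used to estimate GFR.

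Make no between-arm comparison of laboratory values or laboratory-detected AEs. With no scheduled post-baseline labs in standard care, an apparent excess on antimicrobials could simply reflect more testing.

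**Cost.** Some extra programming. If lab values are not already in the database, up to about 900 panels on the planned schedule would need entry, some of them from local laboratories.

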8.3 Three (3) month lab for antimicrobial assigned subjects ONLY

Approximately 3 months (visit window of 3 months +/- 7 days) after enrollment, subjects assigned to the antimicrobial therapy arm will return to the enrolling site or a local laboratory for the following:

- Blood draw for the following safety labs (**Described in Appendix B**):
 - Chemistry panel and liver function tests– defined as minimum of sodium, potassium, chloride, bicarbonate, BUN, and creatinine, total bilirubin, direct bilirubin, alkaline phosphatase, ALT, and AST
 - Complete blood count (CBC)

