## IV. General Methodology

---

Definition of Statistical Significance: The statistical plan will test non-directional hypotheses, i.e., all tests will be 2-sided. The level of significance for all efficacy and safety analyses will be 0.05.

Statistical Tests: For situations where one observation per patient is observed, (e.g. safety comparisons at individual time points), a general analysis convention will be used unless otherwise specified. For continuous and ordinal variables, treatment group differences will be tested using the Wilcoxon rank-sum test for two groups and Kruskal-Wallis one-way analysis of variance for comparisons of more than two groups. For censored data, like time to event, treatment group differences will be tested using the log rank test. For discrete variables, treatment group differences will be tested using the chi-square test. In the situation of low cell counts the treatment group differences will be tested using Fisher's exact method.

Descriptive Statistics: For continuous and ordinal variables the number of observations, number of missing values, mean, standard deviation, median, twenty-fifth percentile, and seventy-fifth percentile will be given. For binary (e.g. yes/no), categorical, and/or ordinal variables a simple count and percent will be provided. Other statistics may be considered if necessary.

Descriptive Plots: Descriptive plots may be produced in addition to descriptive statistics if deemed appropriate. If deemed necessary plots of descriptive statistics such as spaghetti, mosaic, box, cumulative distribution, and loess curves will be provided.

Study Listings: Study data will be listed by treatment group, visit if applicable, and patient where appropriate.

Software and Validation Procedures: All data presented in interim and final analyses will be generated and validated under the guidance of the DCRI Clinical Trials Statistical SOPs.

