### **Concomitant Medication**

Endpoint Description: Frequency and types of concomitant medication usage during the following-up period of the trial.

Response Variable Definition: Concomitant medication will be collected each visit and phone contact with the site.

Statistical Tests: The number of patients with one or more given concomitant medication will be tabulated. Shift tables from baseline will be generate also. Comparison of the “Standard care + oral antimicrobial therapy” and “Standard care” arms will be done with a chi-square test, i.e. the number of patient with one or more occurrences. Other groupings of concomitant medication maybe generated as deemed necessary.

Interpretation of Results: For cases where “Standard care + oral antimicrobial therapy” rate is less than “Standard care” rate will indicate a reduction for “Standard care + oral antimicrobial therapy” arm. For cases where “Standard care + oral antimicrobial therapy” rate is greater than “Standard care” rate will indicate an increase for “Standard care + oral antimicrobial therapy” arm.

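### Non-serious adverse events of special interest reach no planned result, and the SAP's default test, if applied to hyperkalemia, would lean toward apparent harm because potassium is scheduled in one arm only

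*Protocol*

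**What the plan says.** Protocol 10.4 limits collection of non-serious harms: "Adverse events (AEs) of special interest ONLY will be collected for the CleanUP-IPF trial". It names five events: arrhythmia, vomiting, diarrhea, rash and hyperkalemia. "These adverse events of special interest will be collected via data entry into the eCRF within the electronic data capture system", with start and stop dates, and nothing restricts this to one arm.

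SAP IX has two safety endpoints. One is "Frequency and types of serious adverse events (SAEs) during the following-up period of the trial"; the other is "Frequency and types of concomitant medication usage during the following-up period of the trial". The safety mock-ups match: Table 5.1 is for SAEs and Table 5.2 for medication shifts. The addendum of 29 May 2020 changes endpoint adjudication and SAE coding and adds sensitivity analyses by censoring date. None of these mentions the five events.

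The only SAP text that could reach them is the convention in section IV for one observation per patient ("e.g. safety comparisons at individual time points"), which applies unless something else is specified. It says "For discrete variables, treatment group differences will be tested using the chi-square test", with Fisher's exact method for low cell counts and a two-sided 0.05 level for safety as well as efficacy.

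On laboratory tests, Protocol 8.3 is headed "Three (3) month lab for antimicrobial assigned subjects ONLY", and Appendix A, footnote 3, schedules the later panels "For subjects assigned to the antimicrobial therapy arm, a blood sample to document complete blood count, liver function tests, and chemistry panel".

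**The concern.** There are two linked problems.

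The first is coverage. These five events are the only non-serious harms the trial records, and they matter to its own rationale. Protocol 5.3 discusses trimethoprim-related hyperkalemia as a possible route to cardiovascular events, and Protocol 5 lists rash and hyperkalemia among the significant intolerances to co-trimoxazole. The NHLBI letter of December 2019 reports no clear harm signal, but does report a trend toward more primary events, deaths and SAEs in the intervention arm. A reader of the results will want the full harm record, and the plan as written leaves the non-serious part out.

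The second is detection. Hyperkalemia is usually found by measuring potassium, and the protocol schedules that after baseline in only one arm. An analyst who fills the gap with the default test would compare risk and detection together, and could report a harm signal with no drug effect behind it.

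**Working it through.** The plan gives no figure to reproduce here, so the check has three steps.

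**1. Coverage.** Protocol 10.4, SAP IX, mock-up Tables 5.1 and 5.2 and the addendum were compared. An event of special interest enters a planned table only if it is also serious (Protocol 10.5). The SAP was signed on 28 November 2016 and Protocol Amendment 2 is dated 2 March 2018. That may explain the gap, but the 2020 addendum did not close it.

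**2. Scheduled potassium after baseline** (Protocol 8.1 to 8.8, Appendices A and B). Both arms have baseline chemistry.

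| Time | Co-trimoxazole | Doxycycline | Standard care |
|---|---|---|---|
| Week 1 | 1 | 0 | 0 |
| Month 3 | 1 | 1 | 0 |
| Month 6 | 1 | 1 | 0 |
| Month 12 | 1 | 1 | 0 |
| Month 24 | 1 | 1 | 0 |
| Total | 5 | 4 | 0 |

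The Appendix B blood volumes agree: 28.5 + 6 + 8.5 + 8.5 + 18.5 + 18.5 = 88.5 ml in the antimicrobial arm and 28.5 + 10 + 10 = 48.5 ml in standard care. The difference at months 12 and 24, 18.5 − 10 = 8.5 ml, equals the volume for CBC plus chemistry at months 3 and 6. (Protocol 8.1 contradicts itself on who has the week 1 test: the heading says co-trimoxazole only, the text says the antimicrobial arm. The two must be reconciled; either way standard care has none.)

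**3. Size of the bias if the default test were used.** From the documents: about 500 patients randomized 1:1, so n = 250 per arm, and a two-sided 0.05 level. Assumed, because the documents give neither: the true risk p, equal in both arms, and the fraction s of cases detected in standard care, with full detection in the antimicrobial arm.

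Observed counts are X ~ Bin(250, p) and Y ~ Bin(250, s·p). The test rejects if

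|X − Y|/n ÷ √[ p̄(1 − p̄)·2/n ] > 1.96, where p̄ = (X + Y)/(2n).

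The rejection probability is the sum of the joint binomial probabilities over all rejecting pairs (X, Y). The ratio of expected observed risks is p/(s·p) = 1/s. At p = 5% the expected counts are 12.5 against 9.4, 6.25 and 3.1 for s = 75%, 50% and 25%.

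| True risk in both arms | s = 100% | s = 75% (ratio 1.33) | s = 50% (ratio 2) | s = 25% (ratio 4) |
|---|---|---|---|---|
| 3% | 0.05 | 0.08 | 0.20 | 0.46 |
| 5% | 0.05 | 0.10 | 0.31 | 0.71 |
| 10% | 0.05 | 0.17 | 0.57 | 0.95 |

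With equal detection the test keeps its level, so the excess comes from detection alone. Fisher's exact test, summed over the same pairs, is more conservative but does not remove it: at p = 5% it gives 0.07, 0.24 and 0.61.

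**The case against.** The strongest reply is that the plan contains no biased test. No section specifies a between-arm comparison of hyperkalemia, and section IV is a general convention that names no event. That stands: the bias is a risk the gap invites, not an error already written down.

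It can also be said that harms are covered. Serious cases enter the SAE table by body system and event name with an arm comparison, SAEs include those found by laboratory test (Protocol 10.5), the DSMB reviews safety data, and the SAP lets its templates be modified. This also stands, and it narrows the gap to non-serious events. But DSMB review is not a reported result, and freedom to modify templates is not a plan to analyse these events.

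One-arm safety tests are defensible for patients taking the drugs. Nothing here questions them or asks for more blood draws.

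A reader might infer something stronger: at 5% risk the scheduled tests would record about 12 of 250 cases against 0 of 250, with Fisher p = 0.0004, and no true difference. The documents do not support this as the expected result. It assumes that standard care detects nothing, whereas all participants are followed under usual care (Protocol 8) and events of special interest are collected without restriction by arm. It is the limit of the range. Five tests is likewise a maximum: doxycycline patients have four, and with a planned minimum follow-up of 12 months not everyone reaches month 24.

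**Conclusion.** The point holds in two parts of different strength. The omission is a fact of the documents: non-serious events of special interest are collected and have no planned analysis.

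The bias is conditional on someone applying the default test to hyperkalemia. Its direction, toward apparent harm in the antimicrobial arm, follows from the schedule provided usual care detects fewer cases than scheduled testing. Its size cannot be derived from the documents. Over assumed standard-care detection of 75% to 25%, the false-positive probability runs from 0.08 to 0.46 at 3% risk, 0.10 to 0.71 at 5% and 0.17 to 0.95 at 10%, against a nominal 0.05.

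It would go too far to say that the trial's harms go unreported, since serious events are tabulated, or that the SAP plans an invalid hyperkalemia test. The primary endpoint, sample size and error control are not affected. The change should be made because it completes the harm reporting at little cost.

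**What to change.** Add to SAP IX:

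- One table of each adverse event of special interest by arm and by assigned agent, giving patients with at least one event and event counts.
- Laboratory-detected hyperkalemia reported descriptively within the antimicrobial arm, with no between-arm p-value.
- Any between-arm hyperkalemia comparison limited to events meeting SAE criteria.
- A footnote stating that post-baseline potassium was scheduled in the antimicrobial arm only, and that SAEs may also be found by laboratory test, so even this comparison is not wholly free of unequal detection.
- The definition of hyperkalemia used for the table. The documents give a potassium cut-off only for eligibility and choice of agent, none for the adverse event.

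Do not compare arms on hyperkalemia found outside the scheduled tests. Scheduled draws would find many antimicrobial-arm cases first, and removing those depletes one arm only. As an illustration with every value assumed, take true risks of 10% and 5%. If scheduled draws find 80% of antimicrobial-arm cases, at most 10% × 0.2 = 2% remain. If usual care finds half of the standard-care cases, 5% × 0.5 = 2.5% are seen. The observed ratio is then at most 2/2.5 = 0.8 when the true ratio is 2, which would hide harm. The protocol also records event dates but not how an event was detected.

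The cost is one more table from data already collected. The downside is that the between-arm hyperkalemia comparison will rest on few events.
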